## 3. Study Design

## 3.1 Part 1 (CHICO)

## **Design overview**

#### BAY No. A2502/IMPACT No. 16027 Page: 7 of 30

This is a Phase 3, prospective, randomized (to dosing regimen), age-stratified, double-blind, parallel-group study to evaluate the efficacy, safety/tolerability, and PK of oral administration of nifurtimox in children with a diagnosis of Chagas' disease. A schematic of the study design is presented in Figure 3-1.

#### Figure 3–1. Study Design of Part 1

D = Day, EOT = end-of-treatment, V = Visit.

a At Visits 4, 5, and 7, study site personnel will contact the subject/legally authorized representative via telephone to assess for the occurrence of AEs, use of concomitant medications, and compliance with study drug administration. If any safety concern arises, subjects may return to the study site for an Unscheduled Visit.
b Subjects who discontinue prematurely from study drug administration will continue to return to the investigational site for study assessments at Visits 3, 6, and 8 (EOT), and undergo telephone assessments as described for Visits 4, 5, and 7. If subjects are unable/unwilling to do so, they must return to the investigational site 30 (±3) days after the last dose of study drug for EOT (Visit 8) assessments, and undergo telephone assessments as described for Visits 4, 5, and 7. If the subject is unable/unwilling to return to the clinic for the EOT Visit 8), then a telephone assessment as described for Visits 4, 5, and 7. If subjects is unable/unwilling to return to the clinic for the EOT Visit 8), then a telephone

assessment as described for Visits 4, 5, and 7 may be performed in lieu of Visit 8 assessments.

In this study, approximately 300 pediatric subjects will be randomized (2:1 randomization, 60-day regimen vs. 30-day regimen). Subjects will be stratified by age at randomization into four strata as specified below:

- Stratum 1: 0 to 27 days
- Stratum 2: 28 days to younger than 8 months
- Stratum 3: 8 months to younger than 2 years
- Stratum 4: 2 years to younger than 18 years

A minimum of 38 subjects in each age stratum is targeted, but not required, in order to be able to derive meaningful safety conclusions. Enrollment will continue until this specification is

met, unless it is determined that such a target would be unlikely to be reached in a reasonable time.

After study eligibility has been confirmed and safety assessments have been performed at Visit 2 (Day 1), subjects will be randomized via Interactive Voice Response System/Interactive Web Response System (IVRS/IWRS) in a 2:1 ratio (60-day regimen vs. 30-day regimen) to one of two treatment groups:

- Nifurtimox tablets administered three times daily for 60 days (Days 1 60, active nifurtimox treatment, Treatment Group 1) or
- Nifurtimox tablets administered three times daily for 30 days, followed by nifurtimox placebo administered three times daily for 30 days (Days 1 30, active nifurtimox treatment; Days 31 60, placebo; Treatment Group 2).

The study is composed of 3 periods:

- Screening period
- Treatment period
- Follow-up period

## **Treatment period**

The first dose of study drug will be administered at Visit 2. Pre- and post-dose PK blood samples will be obtained at specified time points from those subjects consenting to PK assessments. At the 2 - 4 hour time point of PK blood sampling (i.e., at the time of maximum concentration  $[C_{max}]$ ), an ECG (optional for subjects < 5 years of age at the discretion of the investigator) will be obtained to allow for PK/PD investigations. Study drug will be dispensed, and instructions for study drug administration will be provided to all subjects.

Subjects will return to the investigational site for efficacy and safety assessments at Visit 3 (Day 7±1) and Visit 6 (Day 30). Subjects who have not consented to PK assessments will take that day's doses of study drug as instructed. Subjects consenting to PK assessments must hold the morning dose of study drug; for these subjects, a pre-dose PK blood sample will be obtained, then the morning dose of study drug will be administered. Post-dose blood samples will be obtained at specified time points, and ECGs will be obtained at the 2 - 4 hour post-dose time point. A pre-paid phone card will be provided to all subjects to facilitate contact between study site personnel and the subjects/subjects' authorized representatives.

At Visit 6 (Day 30), subjects will return all remaining study drug and empty packaging, and study drug for the remaining 30 days of treatment will be dispensed.

Visits 4 (Day 14), 5 (Day 21), and 7 (Day 42) will be telephone assessments where study site personnel will contact the subject/legally authorized representative via telephone to assess the

occurrence of AEs, use of concomitant medications, and compliance with study drug administration. A Phone Contact Form for the telephone assessments will be provided to all sites.

Subjects will return to the investigational site for efficacy and safety assessments on Day 60 (Visit 8), which will be the EOT for both treatment groups. Subjects who have not consented to PK assessments will take that day's doses of study drug as instructed. Subjects consenting to PK assessments must hold the morning dose of study drug. A pre-dose PK blood sample will be collected, then the morning dose of study drug will be administered. Post-dose PK blood samples will be obtained at specified time points, and ECGs will be obtained at the 2 - 4 hour post-dose time point. Study drug will be collected, and no additional study drug will be dispensed.

## Follow-up period

After the EOT visit (Visit 8), subjects will return to the site on Days 90 (Visit 9), 240 (Visit 10), and 420 (Visit 11) for additional efficacy and safety assessments. The total duration of each subject's participation is expected to be approximately 14 months.

#### Primary variable(s)

The primary efficacy variable will be sero-reduction or sero-conversion at 12 months posttreatment using two conventional ELISA serology tests as the measure of efficacy.

## End of part 1 of the study

The end of part 1 of the study as a whole will be reached as soon as the last visit of the last subject has been reached in all centers in all participating countries.

## **3.2** Part 2 (CHICO SECURE)

#### **Design overview**

This is a prospective, long-term follow-up of subjects, who were randomized and received at least one dose of their assigned 60- or 30-day nifurtimox treatment. The study is designed to evaluate seronegative conversion and serial reduction in OD measured by ELISA.

Subjects will be followed up for a total of 4 years after end of nifurtimox treatment. The first year of follow-up period is included in part 1 and 3 years of follow-up are included in part 2 of the study.

The following age categories will be considered for part 2 of the study:  $\leq 2$  years,  $\geq 2$  years to  $\leq 6$  years,  $\geq 6$  to  $\leq 12$  years,  $\geq 12$  to  $\leq 18$  years (age is defined as subject's age at randomization).

Subjects enrolled will be followed annually with visits to the investigational site. Seronegative conversion will be measured by two types of assay, recombinant ELISA and IHA. For assessment of serial reduction compared to baseline defined as screening visit of part 1 (Visit 1), OD will be measured by recombinant ELISA and total purified antigen ELISA.

The first visit should be performed as soon as possible after availability of regulatory and ethics committee approval for all subjects who have already completed part 1 of the study for 1 year  $\pm$  6 weeks or longer. Subjects who are entering the study beyond the time window for FU Visit 1 (2 years  $\pm$  6 weeks) will have their eligibility assessments as soon as possible provided that consents/assents have been obtained. Subjects will have annual visits at the investigational site for efficacy and safety assessments for 3 years. Timing of study visits is relative to end of treatment in part 1 of the study.

Between the annual visits at the investigational site, subjects and/or his or her parent(s) or legally authorized representative(s) will be contacted by qualified personnel by a method agreed (eg. phone call) about 6 months after a visit at the investigational site to identify the occurrence of potential clinical symptoms of Chagas' disease or any pathology mentioned in the exclusion criteria using a structured interview. In case of suspected findings, an unscheduled visit at the investigational site to initiate appropriate diagnostic evaluations will be requested.

## Primary variable

The primary efficacy variable will be the incidence rate of seronegative conversion measured by two types of assay (recombinant ELISA and IHA) in subjects who were randomized and received at least one dose of the 60-day nifurtimox treatment regimen. Both test results should be negative for the subject to be considered as seroconverted.

## End of part 2 of the study

The end of part 2 of the study as a whole will be reached as soon as the last visit of the last subject has been reached in all centers in all participating countries.

## **Primary completion**

The primary completion event for part 2 of the study is last subject last visit (LSLV).

BAY No. A2502/IMPACT No. 16027

Page:

## 4. General Statistical Considerations

## 4.1 General Principles

The statistical evaluation will be performed using the software package SAS release 9.2 or higher (SAS Institute Inc., Cary, NC, USA). Unless otherwise specified, all significance tests will be conducted using a 2-sided alpha level of 0.05, and confidence intervals (CIs) will be 2-sided 95% intervals. All variables collected in this study will be summarized with descriptive statistics at each assessment time. For continuous variables, descriptive statistics will include the number of data available and missing data, means, standard deviations, medians, minimums, and maximums. For categorical variables, frequency counts and percentages will be provided. These will be calculated for each age stratum by treatment regimen, as well as the overall set of study subjects.

## 4.2 Handling of Dropouts

A subject who discontinues study participation prematurely for any reason is defined as a "dropout" if the subject has already been randomized, assigned to treatment, and administered at least one dose of study drug.

A subject who, for any reason (e.g., failure to satisfy the selection criteria), terminates the study before the time point used for the definition of "dropout" is regarded as a "screening failure".

Depending on the time point of withdrawal, a withdrawn subject is referred to as either "screening failure" or "dropout". A subject who is withdrawn from the study will not be replaced.

Subjects who discontinue prematurely from study drug administration will continue to return to the investigational site for study assessments at Visits 3, 6, and 8 (EOT), and undergo telephone assessments as described for Visits 4, 5, and 7. If subjects are unable/unwilling to do so, they must return to the investigational site 30 ( $\pm$ 3) days after the last dose of study drug for EOT (Visit 8) assessments, and undergo telephone assessments as described for Visits 4, 5, and 7. If the subject is unable/unwilling to return to the clinic for the EOT Visit (Visit 8), then a telephone assessment as described for Visits 4, 5, and 7 may be performed in lieu of Visit 8 assessments.

Premature discontinuations from study drug will be summarized by treatment regimen, both for any type of discontinuation, and for each specific reason for discontinuation.

## 4.3 Handling of Missing Data

#### Part 1 (CHICO)

No imputations will be made for missing values occurring in the safety and background variables. Background variables include demographics (sex, age), height/length, weight, medical/surgical history, and medication history.

All efforts will be taken to collect all data. However, despite best efforts, it may be inevitable that missing data are reported. In the primary efficacy analysis done on the full analysis set (FAS), subjects who have missing conventional serology results at the 12 month time point will be treated as failures (i.e. no cure).

For the secondary analysis using the per-protocol set (PPS), all subjects who do not have both conventional serology determinations to assess the 12-month time point will be excluded from the analysis.

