6.3.1 Withdrawal

Withdrawal criteria

Subjects *must* be withdrawn from the study if any of the following occurs:

• At their own request or at the request of their parents' or legally acceptable representative. At any time during the study and without giving reasons, a subject may

	Integrated Clinical Study Protocol	
	BAY A2502 / 16027	
03 NOV 2020	Version 11.0	Page: 40 of 259

decline to participate further. The subject will not suffer any disadvantage as a result of this decision.

- Pregnancy. If any urine pregnancy test is positive, a serum pregnancy test must be performed to confirm the result. See Section 9.6.2.⁹⁴ (not applicable to part 2)
- Subjects, with positive parasitology test at the 30-day visit for whom (1) it has been determined that the drug was administered correctly and (2) the daily dosage given was correct, must be discontinued from the study and treated with an alternative trypanocidal medication, selected by the investigator.⁹⁵ (not applicable to part 2)

Subjects *may* be withdrawn from the study if any of the following occurs:

- If, in the investigator's opinion, continuation of the study would be harmful to the subject's well-being
- At the specific request of the sponsor and in liaison with the investigator (e.g., obvious non-compliance, safety concerns)
- For the following situations that are regarded by the investigator to be related to the use of study drug (nifurtimox) (not applicable to part 2):
 - Severe nervous system disorders such as seizure, vertigo/dizziness, polyneuropathy, or peripheral neuropathy
 - Severe gastrointestinal disorders, severe decreased appetite
 - Significant loss of body weight in the judgment of the investigator
 - Severe hepatic impairment
 - Severe renal impairment
 - Psychic disorders such as disorientation, psychotic behavior
 - Development of malignant disease
 - Hematological abnormalities such as severe leukopenia

Depending on the time point of withdrawal, a withdrawn subject is referred to as either "screening failure" or "dropout" as specified below:

Screening failure

A subject who, for any reason (e.g., failure to satisfy the selection criteria), terminates the study before the time point used for the definition of "dropout" (see below) is regarded as a "screening failure."

Re-starting the defined set of screening procedures to enable the "screening failure" subject's participation at a later time point is allowed only in the following situations (not applicable to part 2):

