9.4.3 Concentration tests for *T. cruzi*

Concentration tests for *T. cruzi* will be performed on all subjects < 8 months of age at randomization at the screening visit, and at Visits 3, 6, 8 and 9.

Details describing the collection, processing, storage and shipment of blood samples, and the concentration test protocol, will be described in a separate manual. Concentration tests for *T. cruzi* will be performed by a local laboratory according to the standard of care for each country.¹⁵⁶

Concentration test for *T. cruzi* is not applicable for subjects in part 2 of the study. However, concentration test for *T. cruzi* may be performed in children born of female study subjects to detect congenital infection (see Section 9.6.2).

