#### Per protocol set (PPS)

The primary analysis will also be done using the per-protocol set, which is comprised of randomized subjects treated with study drug who have no major protocol deviations. Major protocol deviations defined in this study will include:

- Subjects who have both conventional serology results missing at the 12-month time point
- Subjects who do not meet in-/exclusion criteria but entered treatment phase
- Subjects who take less than 80% or more than 120% of total assigned doses of study drug
- Subjects whose treatment codes are unblinded during the study
- Subjects who have taken prohibited medicine during the study

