#### Sensitivity analyses of the primary efficacy variable

The following sensitivity analyses for the primary efficacy variable will be performed:

- Missing values due to the following reasons treated as treatment failures and other missing values excluded from analysis:
  - 1. the reason for discontinuation is known or suspected to be treatment ineffectiveness or an AE,
  - 2. a subject has not had a negative serology at any visit and has no serology determination for the primary analysis visit,
  - 3. an indeterminate or incorrectly performed serology determination occurs at the primary analysis visit (e.g. missing values due to lab procedure, not enough sample materials to perform the test, performance error, etc.).
- Observed data only
- Analysis on PPS

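### The per-protocol analysis drops children whom the protocol withdraws for a positive Day 30 parasitology test, although the full analysis set counts them as failures

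*SAP*

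**What the plan says.** **Withdrawal rule.** Protocol 6.3.1 lists among the mandatory withdrawals "Subjects, with positive parasitology test at the 30-day visit for whom (1) it has been determined that the drug was administered correctly". A right daily dose is the second condition. These children "must be discontinued from the study and treated with an alternative trypanocidal medication, selected by the investigator".

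**Follow-up.** The primary serology is drawn at Visit 11, Day 420 (Protocol Table 9–1). Protocol 5.1 and SAP 4.2 describe continued attendance after early stopping of study drug only at Visits 3, 6 and 8, with phone contacts at Visits 4, 5 and 7. Neither document describes a 12-month visit for a child discontinued from the study.

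**Who is tested.** Protocol 9.4.3 sets the schedule of the concentration test, which "will be performed on all subjects < 8 months of age at randomization at the screening visit, and at Visits 3, 6, 8 and 9". Visit 6 is the Day 30 visit.

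**How the outcome is scored (Part 1).**
- FAS, primary analysis: missing 12-month conventional serology is a failure (SAP 4.3; Protocol 10.3.2.1).
- First sensitivity analysis (SAP 6.2.1.1): failure if the child stopped for known or suspected lack of effect or an adverse event, or has neither a negative serology at any visit nor a 12-month result.
- PPS: SAP 4.3 says that "all subjects who do not have both conventional serology determinations to assess the 12-month time point will be excluded from the analysis". SAP 5.1 lists as major deviations "Subjects who have both conventional serology results missing at the 12-month time point" and intake below 80% or above 120% of assigned doses.
- "Observed data only" (SAP 6.2.1.1): named without further rules.

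**The concern.** The withdrawal criterion first rules out wrong dosing and wrong administration, so what remains is evidence that the drug did not clear the parasite. The child's absence at 12 months is a consequence of that finding. Leaving the child out of the PPS selects subjects on outcome: the analysis loses failures for the very reason that they failed. The SAP counts the same event as no cure in two analyses and as outside the population in a third, and does not explain the difference.

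At stake is the value of the PPS as a check on the primary result. If it gives a higher rate than the FAS, part of the gap may come from this removal and not from good adherence, and the planned output would not show which.

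**Working it through.** **1. The plan's own figure.** Protocol 10.4 gives 99% power with a true cure rate of 55%, n = 200 and success when the lower 95% limit exceeds 16%. SAP 6.2.1.1 sets the limit as p − 1.96·√(p(1−p)/n) − 1/(2n).
- 44/200: 0.2200 − 0.0574 − 0.0025 = 0.1601, which passes.
- 43/200: 0.2150 − 0.0569 − 0.0025 = 0.1556, which fails.

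Success needs at least 44 cures. The exact binomial probability of 44 or more at 55% is above 99.99%, consistent with the stated 99%. (SAP 6.5 still uses 260 in this arm; the cut-off is then 56 and power is again above 99.99%. The protocol's 200 is used below.)

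**2. Does the child leave the PPS?** There are two separate routes.
- Serology: no Visit 11 means neither determination exists. The child is out under SAP 4.3, and also under the narrower wording of SAP 5.1, which requires both results to be missing.
- Dosing: stopping at Day 30 of 60 gives 30/60 = 50% of assigned doses. The ±3-day window on Visit 6 gives 27/60 = 45% to 33/60 = 55%. Reaching 80% would take 0.80 × 60 = 48 days.

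Amending the serology rule alone would therefore not bring the child back.

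**3. Direction.** If the PPS holds x cures among n and m such failures were left out, the rate is x/n without them and x/(n+m) with them. For x > 0 and m > 0 the first is always the larger.

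**4. Size.** The documents do not give m. Assumptions: 110 cures among 200 (the planned 55%), and no other PPS exclusions, so that this effect stands alone. With these children kept as failures the result is 55.0%, lower limit 47.9%, whatever m is.

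| m dropped | Rate | Shift (points) | Lower 95% limit | Cures needed to pass 16% |
|---|---|---|---|---|
| 1 | 110/199 = 55.3% | +0.3 | 48.1% | – |
| 3 | 110/197 = 55.8% | +0.8 | 48.6% | – |
| 5 | 110/195 = 56.4% | +1.4 | 49.2% | 44 |
| 10 | 110/190 = 57.9% | +2.9 | 50.6% | 43 |
| 20 | 110/180 = 61.1% | +6.1 | 53.7% | 41 |

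**5. Scale for m.** The SAP design overview says "A minimum of 38 subjects in each age stratum is targeted, but not required". Two strata lie below 8 months: 2 × 38 = 76 infants, of whom 76 × 2/3 ≈ 51 would be in the 60-day arm. So m = 5 would mean about 10% of them, m = 10 about 20% and m = 20 about 39%.

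**The case against.** The strongest reply is that the plan already treats these children correctly where the conclusion is drawn. The FAS scores them as no cure, the first sensitivity analysis does the same, and the benznidazole comparison in SAP 6.2.1.3 reuses the primary interval. That stands. A reader might infer that the trial's claim of efficacy is inflated; the documents do not support this.

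A reader might also infer that the supportive analyses can only come out higher than the FAS. For the PPS that is wrong. SAP 5.1 also removes subjects for eligibility violations, intake outside 80–120%, unblinding and prohibited medicine. Some of them may be cured, so the net shift can go either way. Only the contribution of the Day 30 withdrawals has a fixed sign.

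The observed-data analysis is a different matter. A complete-case rate cannot be below a rate that counts every missing result as failure; that contrast is its purpose. Inserting failures without 12-month serology would contradict its name and largely repeat the first sensitivity analysis. Its definition should stay.

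The primary variable is 12-month serology, and Protocol 6.3.1 does not itself label the withdrawn child as not cured on it. That is true, but the FAS already gives that label, so using it in the PPS brings in no new endpoint.

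Finally, the size is assumed and probably small, and the restriction to infants is an inference. Protocol 6.3.1 does not define the parasitology test, and qPCR is also scheduled at Visit 6 for all ages. A footnote to Table 9–1 says the qPCR specimens are stored, which makes the infant-only reading plausible without settling it. The SAP specifies no PPS or observed-data result by age stratum, so a claim that infants would show 100% cure in those analyses has no planned output behind it.

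**Conclusion.** The point holds for the PPS and is of modest weight. A failure that the protocol itself acts on leaves the PPS through two exclusion rules, while the FAS and the first sensitivity analysis count it. On the planned 55% of 200, the isolated effect is +0.3 points for one such child, +1.4 for five and +2.9 for ten. The 16% criterion is touched only near its cut-off: the cures needed fall from 44 of 200 to 43 of 190 with ten withdrawals. The primary conclusion and the benznidazole comparison do not move.

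This rests on three things that the documents do not state outright:
- 12-month serology will be absent, which is inferred from discontinuation from the study and the visit schedule;
- intake will be below 80%, which is probable given a stop near Day 30;
- the number withdrawn, which is assumed throughout.

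The effect should fall mainly on infants under 8 months, but not certainly on them alone.

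**What to change.** In SAP 4.3 and 5.1, state that a subject withdrawn under the Day 30 positive-parasitology criterion of Protocol 6.3.1 stays in the PPS and is scored as no cure. This must apply notwithstanding both the missing-serology exclusion and the exclusion for less than 80% of assigned doses, unless the subject has another major deviation. The same sentence should make clear that the alternative drug given because of the withdrawal does not itself count as prohibited medicine.

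Leave the observed-data analysis as complete-case. Beside it, report the number of these withdrawals by regimen and age stratum. SAP 4.2 already tabulates study-drug discontinuations by reason and regimen, so this adds the age split and a separate category.

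The cost is one sentence, one programming condition and one table row. Protocol 6.3.1 already requires the reason for withdrawal to be recorded in the eCRF. The downside for the sponsor is a slightly less favourable PPS rate. The withdrawal rule itself is not changed.
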